4.3 Inclusion of Subjects using Marijuana

The incidence of cannabis use in early psychosis patients in the US is estimated at 40% to 60% and a serious concern has been raised that excluding individuals who use cannabis may bias samples and make results less generalizable to clinical populations [51]. There is no reason to expect a negative interaction between cannabis and levetiracetam (no pharmacokinetic or pharmacodynamic interaction). Because treatment is randomized, the two treatment groups should be balanced in terms of cannabis use. We will record past use of cannabis and urine toxic screen results for cannabis at screening in addition to self-report of cannabis during the trial and will include this as a factor in our analysis to assess whether cannabis use influences response to levetiracetam.

We sought consultation from other investigators working in the area of early psychosis and from our DSMB and have adopted exclusionary criteria for cannabis use consistent with their recommendations. These new criteria are based on the Diagnostic and Statistical Manual (DSM) 5 which revised the classification for cannabis use from abuse & dependence to cannabis use disorder, mild, moderate or severe. Criteria are provided for each category. We would like to adopt these criteria for the current study and future studies:

1. Exclude individuals with moderate or severe cannabis use disorder.

CONFIDENTIAL

2. Exclude individuals who report having used cannabis within 72 hours of the MRI scan.
3. Include individuals with mild cannabis use disorder

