There are no known interactions between tetrahydrocannabinol (THC), cannabidiol (CBD) or other phytocannabinoids and levetiracetam. Levetiracetam is not metabolized by the hepatic cytochrome P450 system, so pharmacokinetic interactions are unlikely. THC may transiently worsen psychosis in some patients and CBD may improve psychosis; whether THC-associated worsening of psychosis responds to antipsychotics is unclear—the data are inconsistent. Similarly, it is not known whether THC-associated worsening of psychosis will improve with levetiracetam. Participants using THC will be notified of this risk.

CONFIDENTIAL

1.5.2 Risks of MRI:

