4.2 Exclusion Criteria

1. Current substance abuse / dependence for substances other than nicotine and THC, (i.e. alcohol, amphetamines, barbiturates, etc.)
 - a. A positive urine toxic screen (excluding THC, tricyclic antidepressants, or benzodiazepines (if prescribed)).
 - b. Moderate or severe cannabis use disorder.
2. Diagnosis of major mood disorder or other Axis I disorder other than schizophrenia, schizoaffective disorder or schizophreniform disorder.
3. Current or recent suicidal ideation-- suicidal ideation with intent or plan (indicated by affirmative answers to items 4 or 5 of the Suicidal Ideation section of the baseline C-SSRS) in the 6 months prior to screening or subjects who represent a significant risk of suicide in the opinion of the investigator.
4. Pregnant or nursing or positive urine pregnancy test.
5. Significant medical or neurological illness by history or physical exam, including seizure disorder, history of loss of consciousness related to head trauma or developmental disorder including mental retardation.
6. Renal insufficiency (if serum creatinine greater than laboratory limits for normal, estimated creatinine clearance must be greater than 80).
7. Contraindication to MRI: Metal implants, pacemaker, or other metal in the body or claustrophobia. Individuals with tattoos will be excluded from imaging if tattoos cover more than 5% of the body surface, if a tattoo is greater than 20 cm, or if a tattoo is located on the face, neck or genitals. Individuals with a contraindication to MRI may participate in the trial but will be excluded from the elective MRI component.
8. Significant history of serious violence
 - a. For both inpatient and outpatient subjects, a history of serious violence as assessed by the Buss-Perry Aggression Questionnaire
 - b. For outpatient subjects only, a score of 5 (moderately severe) or higher on the BPRS hostility item at screening or baseline

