6.9 Drug and Pregnancy Tests

A rapid urine drug screen and (for individuals assigned female at birth or with childbearing potential of childbearing age) a urine pregnancy test will be conducted by the research coordinator / research assistant or by clinical staff during the screening visit. The rapid urine pregnancy test will be repeated at the week 6 study visit. These results will be reviewed at the time of the visit with the study MD or NP. These results will be confirmed by also submitting urine samples to outpatient labs.

At each study visit, a pregnancy prevention questionnaire will be administered. At the screening, week 6 and week 12 visits, a cannabis use questionnaire will be administered to assess cannabis use.

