Appendix 1: Schedule of Events EP Participants

	Screening, Visit 1	Baseline	Week 2	Week 3	Week 4	Week 6	Week 8	Week 12	Follow-Up
	Days -28 to 0	Day 1	Day 6-10	Day 13-17	Day 20-24	Day 34-38	Day 48-52	Day 76-80	Day 85-93
Consent	X								
Authorization Form	X								
Inclusion/Exclusion Checklist	X								
Medical History	X								
Physical Exam	X								

CONFIDENTIAL

This material is the property of the NYU School of Medicine and Langone Medical Center. Do not disclose or use except as authorized in writing by the study sponsor

Psychiatric History	X								
Psychotropic Medication History	X								
DCF	X							X	
SOS	X								
Demographics	X								
EHI	X								
Concomitant Medications	X		X			X		X	
Vital signs	X		X			X		X	X
Anthropometrics	X								
Clinical laboratory assessments (Blood)	X							X	
Biomarkers^		X				X		X	
Urine Drug Screen	X								
Pregnancy Test	X					X			
Randomization		X							
Study drug dispensation		X	X	X	X	X	X	X	
SCID	X								
BPRS	X	X	X	X	X	X	X	X	
SANS		X	X	X	X	X	X	X	
CDSS		X				X		X	
C-SSRS	X	X	X	X	X	X	X	X	
CGI		X	X	X	X	X	X	X	X
BPAQ	X								
Cannabis Use Questionnaire	X					X		X	
Pregnancy Questionnaire	X	X	X	X	X	X	X	X	
SAFTEE		X	X	X	X	X	X	X	X
MCCB*		X				X		X	
Medical Monitoring		X							
Brain Imaging*		X						X	
Levetiracetam blood levels		X**				X		X	
Adverse Event Form		X	X	X	X	X	X	X	X
Study Completion Form									X

* These assessments may be completed within 7 days of the baseline visit.

** These assessments are completed only if participant opts into the optional R61 MRI imaging (see section 6.8)

^ Biomarkers should be collected prior to that day's medication dose

CONFIDENTIAL

This material is the property of the NYU School of Medicine and Langone Medical Center. Do not disclose or use except as authorized in writing by the study sponsor

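### Section 4.3 counts cannabis use reported after randomisation in the factor for response to levetiracetam, so that effect-modification analysis need not be a randomised comparison

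*Protocol*

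**What the plan says.** Cannabis users are eligible. Protocol section 4.2 excludes "Current substance abuse / dependence for substances other than nicotine and THC", and section 4.3 adds "Include individuals with mild cannabis use disorder". Moderate and severe cannabis use disorder are excluded.

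Section 4.3 supports this with a balance argument: "Because treatment is randomized, the two treatment groups should be balanced in terms of cannabis use". It then lists three things to be recorded: past use, the urine result at screening, and use reported on study. The sentence runs on: "in addition to self-report of cannabis during the trial and will include this as a factor in our analysis". The stated purpose is "to assess whether cannabis use influences response to levetiracetam".

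Section 6.9 fixes the timing: "At the screening, week 6 and week 12 visits, a cannabis use questionnaire will be administered to assess cannabis use". The row "Cannabis Use Questionnaire" in Appendix 1 agrees. The urine drug screen appears once, at screening.

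Section 1.5.1 links cannabis to the outcome domain in cautious terms: "THC may transiently worsen psychosis in some patients and CBD may improve psychosis".

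Sections 7.2 to 7.4 name the terms of the primary, secondary and tertiary models. Cannabis is in none of them.

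**The concern.** The balance argument holds for use before randomisation. It does not hold for use reported at weeks 6 and 12, which comes after the drug has had time to act. The pronoun *this* in section 4.3 has a loose antecedent, but on-trial self-report is the nearest item and nothing limits the factor to screening data.

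On-trial use may follow symptoms or side effects, and the trial's hypothesis is that levetiracetam changes symptoms. If use responds to treatment, then among users (and among non-users) the two arms no longer contain comparable people. A treatment effect adjusted for on-trial use, or reported separately for users and non-users, then mixes the drug's effect with this selection. At stake is what the trial says about whether cannabis users respond differently. On-trial use also rests on self-report alone, since no urine screen is scheduled after screening.

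**Working it through.** **The plan's own figure.** The cannabis analysis has none. The design figure in section 7.5 reproduces: √(3/56) × (1.96 + 0.84) = 0.648, with 28 controls and 84 in total. This point does not touch it.

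**Timing.**

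| Component of the factor | When measured | Balanced by randomisation? |
|---|---|---|
| Past use | Screening | Yes, in expectation |
| Urine THC | Screening | Yes, in expectation |
| Questionnaire | Screening | Yes, in expectation |
| Questionnaire | Weeks 6 and 12 | Not guaranteed |

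**Size.** The protocol gives no figure for how use depends on symptoms or treatment, so every simulation input here except the 2:1 allocation and the NYU share is an assumption. Let U ~ N(0,1) be symptom course and T the arm (2:1). On-trial use is C = 1 if λU + e + sT > 0, with e ~ N(0,1), so placebo use is 50%. The outcome is Y = ρU + √(1 − ρ²)ε, with **no** drug effect. I regressed Y on T and C, with 2,000,000 simulated subjects per scenario. The true answer is 0. Cells give λ = 0.5 / λ = 1.0, with ρ = 1:

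| s | Treated use | Adjusted arm effect (SD) | Spurious interaction (SD) |
|---|---|---|---|
| 0 | 50% / 50% | 0.00 / 0.00 | 0.00 / 0.00 |
| −0.25 | 41% / 43% | 0.06 / 0.08 | 0.00 / 0.00 |
| −0.5 | 33% / 36% | 0.13 / 0.16 | 0.02 / 0.02 |
| −0.8 | 24% / 29% | 0.19 / 0.25 | 0.05 / 0.04 |

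Variations:

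- **Weaker link to outcome.** With ρ = 0.6 the adjusted error over the same shifts is 0.04 to 0.15 SD. A logistic model for use with ρ = 0.6, and treated use falling to between 40% and 28%, gives 0.03 to 0.10 SD.
- **Use confined to NYU.** NYU supplies 28 of 84 participants, and Shanghai use is not stated. With 50% placebo use at NYU only and site in the model, the adjusted error is 0.02 to 0.08 SD (ρ = 1) or 0.01 to 0.05 SD (ρ = 0.6). The error among users does not shrink in the same way, because it is a comparison inside NYU. The interaction stays at or below about 0.05 SD if treatment-by-site is also fitted. With a site main effect only, users are compared mainly with Shanghai non-users, and it reaches 0.23 SD in the most extreme scenario.
- **Change through symptoms only.** Take an assumed true effect of −0.65 SD, with use driven only by on-treatment symptoms. Treated use falls to 39% or 32%, and the adjusted effect becomes −0.57 or −0.45, an error of 0.08 to 0.20 SD. No direct drug effect on cannabis use is needed.
- **Pre-randomisation factor.** With use fixed before allocation, both the adjusted error and the spurious interaction are 0.00.

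**Precision of the interaction.** SE = √[(1/28 + 1/56)(1/p + 1/(1 − p))]. At p = 0.5 this is √(0.05357 × 4) = 0.463, and at p = 0.4 or 0.6 it is 0.472. Power for an interaction of 0.65 SD is Φ(0.65/0.463 − 1.96) = 29%, or 28% at SE 0.472. The interaction detectable with 80% power is about 2.8 × 0.463 = 1.3 SD.

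**The case against.** The strongest reply is that section 7 names its model terms and cannabis is not among them. A reader might infer from section 4.3 that the primary comparison is conditioned on on-trial use. The documents do not support that, and the sizes above should not be set against the design effect of 0.65, which belongs to a test with no cannabis term.

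Second, section 4.3 is loose. It does not say how the three measures are combined or which model takes them, and such coding is often left to an analysis plan. This stands in part. But the text does name on-trial self-report as part of the factor, and a plan that followed it would carry the problem over.

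Third, the stated question is effect modification, and the interaction moves far less than the adjusted effect. That is right when use is spread across the trial, or when treatment-by-site is fitted. The effects within users and within non-users, which would normally be reported beside the interaction, still shift. In the simulated direction (treatment lowers use, and use goes with worse symptoms) the drug looks worse, so this would not manufacture efficacy.

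Fourth, nothing in the protocol shows that levetiracetam changes cannabis use, and section 1.5.1 says only that THC may worsen psychosis transiently in some patients. Both are correct. The bias is conditional, and halving of use is an extreme case.

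A reader might also infer that cannabis cannot be told apart from site. That does not follow. At the 40% to 60% US rate quoted in section 4.3, about 11 to 17 of the 28 NYU participants would be users (28 × 0.4 = 11.2; 28 × 0.6 = 16.8), so use varies within that site.

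**Conclusion.** The point holds, confined to the cannabis effect-modification analysis. Section 4.3 puts a post-randomisation measure into the factor and defends it with an argument that covers pre-randomisation use only. If treatment changes use, directly or through symptoms, effects adjusted for on-trial use or compared within its levels are not randomised comparisons. If treatment does not change use, this bias is absent.

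Under the assumed inputs the adjusted effect is off by roughly 0.01 to 0.25 SD, at the lower end if use is confined to NYU. The interaction term moves by at most about 0.05 SD, provided treatment-by-site is fitted where use is concentrated at one site. The primary and other section 7 analyses, as written, are not affected. This is worth correcting because the change is small, not because the trial's main conclusion depends on it.

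**What to change.** In section 4.3, define the effect-modification factor from pre-randomisation data only: past use, screening urine THC and the screening questionnaire. Label the treatment-by-cannabis analysis exploratory and include site in that model, preferably with treatment-by-site because use may differ between the two centres. Report week 6 and week 12 self-report descriptively by arm, and label any analysis that uses it as non-randomised. Carry one matching sentence into section 7, which does not mention the cannabis analysis at present.

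The cost is a few sentences, since all the data are already scheduled. There is a small downside. A screening factor does not address concurrent use, and section 1.5.1 leaves open whether worsening related to THC would respond to levetiracetam. The interaction also has low power at N = 84 (28% to 29% for 0.65 SD), so a null result should not be read as showing no effect modification.

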4.4 Vulnerable Populations

The inclusion of children for this research is necessary as early psychosis often affects individuals under the age of 18. For underage individuals, the treating clinicians will ask the potential subjects and their guardians if they would like to speak to a researcher and both will be required to complete the consenting process. Patients and/or their guardians will have an opportunity to discuss involvement in the study with their treating clinician prior to enrollment. The clinician obtaining the informed consent will take steps to ensure that the participant and his/her guardian are capable of consenting and participating in the study. The clinician will ensure that the individual understands the content and procedures of the study, their rights as a participant, and their right to discontinue participation at any time. Individuals who are not able to demonstrate this level of comprehension will be excluded from participation. As described previously, the potential subject must also achieve a perfect score on a ten-item true/false quiz that asks questions about the study procedure and potential risks. Those who are deemed to lack the capacity to consent will not be enrolled in the study. Minors who turn 18 while in the study will be re-consented as adults.

Students will be informed that if they elect to participate in this study, they can choose to/not to participate or withdraw at any time without any impact on their grades or academic standing.

4.5 Subject Recruitment and Screening

Participants will be help-seeking males or females, ages 16-40, with early psychosis within 5 years of onset, meeting diagnostic criteria for schizophrenia, schizoaffective disorder or schizophreniform disorder and currently exhibiting at least moderate psychotic symptoms defined by a score of 4 or greater on at least one psychosis item of the BPRS (conceptual disorganization, suspiciousness, hallucinations, unusual thought content, grandiosity) with persistence of at least 4 days per week for at least 4 weeks despite antipsychotic treatment for at least 8 weeks and in the absence of psychotomimetic substance use or other potential organic etiologies, or major mood disorder, and in the absence of suicidal ideation, pregnancy, or significant medical illness (including epilepsy).

Referring clinicians will receive the "Information for Clinicians" document, which contains information about the study as well as contact information for the study team.

At the Bellevue Comprehensive Psychiatry Emergency Program (CPEP) or Inpatient Psychiatry Units or Adult Outpatient Psychiatry Clinic as well as the Children's Comprehensive Psychiatric Emergency Program (CCPEP) and Child and Adolescent Psychiatry Inpatient Unit, the staff will identify patients with early psychosis who are appropriate for study participation and willing to speak to an investigator. The study team will access EPIC to determine the participant's initial eligibility. A psychiatrist, psychologist or nurse practitioner on the clinical team will assess the clinical appropriateness of the individual to participate in research and will assess the individual's capacity to consent. A study MD or NP will also perform an assessment of clinical appropriateness and capacity to consent for any individuals interested in participating and will document this assessment. After a potential study participant agrees to sign consent, the remaining screening procedures will take place in the Bellevue CPEP, CCPEP, or on the Bellevue adult or child psychiatry inpatient unit or outpatient clinics. Following the screening procedures, individuals who qualify to participate and who are judged by their clinicians to be safe and appropriate for

CONFIDENTIAL

transportation and imaging, will be transported to the NYU Center for Biomedical Imaging (at [name]) or the NYU CBI (at Washington Square) for the imaging procedures via ambulance or ambulet as per the existing protocol to transport patients within Bellevue for clinical procedures if the patient is inpatient; if the patient is an outpatient a car service will be provided to them at no cost.

Additionally, patients will also be recruited at NYU Langone Health medical centers in Manhattan and Brooklyn, and NYU student health. For participants referred from the Tisch emergency room and the Tisch inpatient psychiatry unit (HCC-10), study staff will follow the same protocols outlined above for Bellevue. Clinicians will be asked to only refer individuals who they believe are appropriate for the study and who are capable of deciding to participate. Once referrals are given, the study team will access EPIC to determine the participant's initial eligibility. Additionally, the study team will use NYU's DataCore service to gather information from EPIC for current NYU patients who may be eligible. [name] and the study coordinator will maintain relationships with clinicians at these institutions in order to generate referrals.

We will include individuals who speak Spanish as potential participants. In order to recruit Spanish speaking patients, our team will receive referrals from clinicians from our network of NYU-affiliated institutions. Clinicians who refer Spanish speaking patients will initially determine if the subject will be eligible to participate our study. If the patient qualifies and agrees to participate in our study, our team will provide a native Spanish speaking interpreter with training and understanding in medical terminology during the study visits.

In China, First Episode Psychosis participants will be recruited from the First Episode Psychosis Program of Shanghai Mental Health Center under the direction of [name]. Clinicians will be asked to only refer individuals who they believe are appropriate for the study and who are capable of deciding to participate. Potential subjects identified by the initial treating clinicians will be asked whether they would like to speak to a researcher. If the patient agrees, the initial treating clinician will then contact the study psychologist or trained study team member and they will determine whether the study clinician (psychologist or psychiatrist) will go and meet with the patient at that time or whether the patient will be scheduled to return for a screening visit with the research team.

Shanghai Mental Health Center was established in 1935 and has 1875 psychiatric inpatient beds of which 80 are dedicated to medication naïve first episode schizophrenia and is staffed by 258 psychiatrists and 581 psychiatric nurses. More than 200,000 psychiatric outpatient visits are recorded each year.

4.6 Subject Consent and Assent

All subjects will be evaluated by a NP or MD for capacity to consent and safety / appropriateness to participate. In order to further ensure protection of privacy for this patient population, patients will not be contacted by any member of the research team unless they have agreed to hear about the research process beforehand from the initial treating clinician. Clinicians in the NYU Medical Center Emergency Psychiatric Service and Adult Inpatient Psychiatry Unit, Bellevue Hospital CPEP and CCPEP, Bellevue Hospital Child and Adolescent Psychiatry Inpatient Unit Walk-in Clinic and Inpatient Units, NYU Student Health Clinic, NYU-Brooklyn (Lutheran) Hospital Emergency Service and Outpatient Psychiatry Clinics (Sunset Terrace), Inpatient Psychiatry Units and the Comprehensive Psychiatry Emergency Program at Bellevue Hospital will be provided with study information as well as a document listing the inclusion/exclusion criteria in order to facilitate recruitment. This will allow the treating clinicians to help identify potential subjects as well as provide interested individuals with basic study-related information. Potential subjects identified by

CONFIDENTIAL

the treating clinicians will be asked whether they would like to speak to a researcher. If the patient agrees, the treating clinician will then contact the study psychologist or trained study team member and they will determine whether the study clinician (psychologist or psychiatrist) or research data associate will go and meet with the patient at that time or whether the patient will be scheduled for a screening. During this meeting, the study will be explained to the potential participant and in the event that the individual is interested in participating, s/he will then be given the consent form to read and review.

Bellevue Psychiatry Adult and Child Inpatient Units and CPEP and CCPEP only: A Bellevue Hospital psychiatrist, psychologist or nurse practitioner will assess the clinical appropriateness of the individual to participate in research and will assess the individual's capacity to consent. A study MD or NP will also perform an assessment of clinical appropriateness and capacity to consent for any individuals interested in participating. After a potential study participant agrees to sign consent, the remaining screening procedures, including the informed consent process (as outlined below), as well as any subsequent study visits will take place on the inpatient unit at Bellevue.

Tisch emergency room / inpatient psychiatry unit (HCC-10): Study staff will receive referrals from NYU clinicians in the emergency room and inpatient psychiatry unit. Study staff will be responsible for assessing the clinical appropriateness of these individuals. After a potential study participant agrees to sign consent, the remaining screening procedures, including the informed consent process (as outlined below), will take place in the emergency room or on the unit. Some outpatients may choose to be electively admitted to HCC-10 at the beginning of the study. Participants choosing to be electively admitted will be allowed to continue participating in the study, and all visits and assessments will take place on the unit.

Process of Consent: Patients who are interested in participating in the study will meet with one of the study MDs or NPs, who will review the consent form and assess the patient's capacity for participation in research in accordance with our standardized research procedures (See CRF for "Assessment of Capacity"). After signing consent, participants will be assessed for eligibility. The study team member will ensure that the individual understands the content and procedures of the study, their rights as a participant, and their right to discontinue participation at any time. Individuals who are not able to demonstrate this level of comprehension will be excluded from participation. In addition, the potential subject must also achieve a perfect score on a ten-item true/false quiz that asks questions about the study procedures and potential risks. After the consent form has been signed, the subject will be provided with a letter detailing study-related information and contact information for key study staff.

Participants who lose capacity during the study will be assessed by the site PI ([name] and [name]) to determine if they should be excluded from the study or if they can safely continue in the study. The PIs will consult with their respective IRBs when making this decision. These decisions will also be reported to the Chair of the DSMB ([name]).

For Spanish Speaking Subjects: Spanish speaking subjects will be provided with certified translated consent forms and assent forms accompanied by a native Spanish speaking interpreter with training and understanding in medical terminology during study visits. The Spanish consent form will be translated and submitted after IRB approval of the study and the English consent form.

Consent Forms: Consent forms will be stored in a locked file cabinet in folders labeled with the patient's study identification number. This file will be separate from any of the subject's study data in order to separate their data from any identifying information.

CONFIDENTIAL

